4.1. Inclusion Criteria

- 4.1.1. Males and females 18 years or older
- 4.1.2. Patients that have already been admitted to ICU (admitted to the ICU for no more than 48 hours before enrollment)
- 4.1.3. Expected to be ventilated at least 48 hours after enrollments.
- 4.1.4. Patient requires enteral feeding (by naso/oro-gastric feeding tube)

4.2. Exclusion Criteria

- 4.2.1. Pregnant women
- 4.2.2. Known anatomical anomalies of the nose, oral cavity, esophagus or the stomach that may prevent/hinder the ability to insert the feeding tube

4.3. Warnings

- Participants may not receive any kind of nutrition given NOT through the feeding tube (or one of its ports)
- MRI- the Feeding tube should be removed before performing the procedure.
- CPR- the feeding tube should NOT be disconnected from the Hub before performing the procedure.

4.4. Initial Screening

All patients already admitted into the ICU who require enteral feeding may be screened for potential enrollment into the study.

Any study procedure can be performed only following ICF signature process, as approved by the local IRB / EC, and in accordance with GCP.

The following information will be recorded in the study eCRF for each patient found eligible to participate in the study, as part of the initial screening:

 ART MEDICAL PATIENT SAFETY TECHNOLOGY	Number: CRO-C-2822	Date issued: 01-Mar-2021
	Rev.06	Page 17 of 35

Subject: smART Plus Comparative Study Protocol - Beilinson

- **Medical history-** During the screening process patient demographic and medical information acquired from the patient or the patient's medical chart, including previous medical history, medications, history of clinically significant abnormalities of all body systems; concurrent diseases; relevant past medical history.
- **Physical Examination-** During the screening process all patients will undergo a physical examination by an authorized physician. The physical examination will include diagnosis and documentation of any significant abnormalities or diseases relevant to the placement and utilization of the feeding tube.
- Inclusion/exclusion criteria
The initial screening information will be recorded in the eCRF for all patients screened to participate in this study.

4.5. Screen Failures

Screen failures are defined as participants who were examined by the PI/Co-investigator as part of the initial screening process and were not subsequently entered to the study (e.g., patient found to be ineligible by the PI/Co-investigator, informed consent was not obtained, PI/Co investigator's discretion, etc.).

A minimal set of screen failure information is required to ensure transparent reporting of screen failure participants, to meet the Consolidated Standards of Reporting Trials (CONSORT) publishing requirements and to respond to queries from regulatory authorities. Minimal information includes patient demographics, screen failure details, eligibility criteria, and any serious adverse event (SAE).

4.6. Enrollment

Patients may be included in the study only if:

- The assessment performed as part of the initial screening (part of the eCRF) is acceptable and patient was found appropriate to participate in the trial, according to the PI (or co-investigator) decision.
- Informed consent has been obtained.
- For women of childbearing age, a negative urine (or blood) pregnancy test.

5. Study Intervention

Following the initial screening procedure and after patient was found to be eligible to participate in the study, patients shall be divided into two study groups:

Group A- ICU patients receiving the investigational device ("Treated")

Group B- Control group, receiving treatment according to local SOC.

The study intervention describes all study procedures and evaluations to be done as part of the study to support the determination of the primary and secondary objectives outlined in this protocol. Study source documents are defined as data collected from patient's medical chart (recorded in the hospital sources) as well as data collected by the smART+ System, as detailed in sections 5.2.8. and 5.3.5. below. In addition, video recording (as detailed in sections 5.2.1. and 5.3.1.) will be also used for later data analysis and serves as source data.

Subject: smART Plus Comparative Study Protocol - Beilinson

5.1. Divisions into Groups

After completion of the “initial screening” chapter in the study eCRF recruitment cycle, and after patient was found likely to participate in the trial, patients will randomly be divided into two groups.

Measures to minimize bias: randomization and blinding

Study participants will be randomly assigned to open-label study groups, in randomization ratio of 1:1.

In this current multicenter trial, the randomization procedures will be centrally organized. The ratio between treated and control groups should be balanced on each site.

In order to promote balanced allocation within the groups, the study randomization shall be stratified according to APACHE score measured at baseline.

To avoid possible bias in the selection and allocation of subjects and to ensure that the randomization is properly maintained throughout the trial, a computer randomization algorithm will be used for subject allocation to each group. The randomization algorithm will be part of the eCRF. Randomization will be implemented by the PI/Co-investigator after initial screening of the patient is completed (and before starting study procedures).

This will allow first of all the selection of suitable patients, and only then division into groups.

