IRB	Institutional Review Board
ISO	International Organization for Standardization
LOS	Length Of Stay

Subject: smART Plus Comparative Study Protocol - Beilinson

ml	milliliter
MOP	Manual of Procedures
NCT	National Clinical Trial
NIH	National Institutes of Health
NIH IC	NIH Institute or Center
NG	Naso-Gastric
PEEP	Positive end expiratory pressure
PI	Principal Investigator
PPI	Proton Pump Inhibitors
QA	Quality Assurance
QC	Quality Control
REE	Resting Energy Expenditure
SAE	Serious Adverse Event
SAP	Statistical Analysis Plan
SOA	Schedule of Activities
SOP	Standard Operating Procedure
VAE	Ventilator Associated Event
APACHE	Acute Physiology and Chronic Health Evaluation

Subject: smART Plus Comparative Study Protocol - Beilinson

1. Protocol Synopsis

Study Title:	Nutrition Monitoring and Feeding Optimization with the smART+ System
Purpose:	To demonstrate the ability of the smART+ System to optimize the delivery of nutrition
Study Design:	Comparative, prospective, stratified randomization
Study Endpoints:	
Primary:
 
Optimization of the delivery of nutrition by the smART+ System as compared to standard of care, by automatically calculating and administering enteral feeding better than standard of care (REE or Calorimeter).
 
Secondary:
 
- Safe use of the entire system (AE/SAE directly related to any of the system components)- Decrease in ICU length of stay from admission to ICU until the decision discharge ordered- Reduction of VAE- Decrease in ventilation days- Decrease in workload related to nurse GRV time- Convenience of use of the system and the user interface (by subjective staff questionnaire)- Assessment of urine flow monitoring related to patient condition and usability
No. of Subjects:	In Beilinson site: 100 patients; 50 patients per group Approximately 200 subjects will be enrolled for the complete multi-center comparative study (100 per group)
Population:	ICU mechanically ventilated patients
Investigational Sites:	Israel, United States, Europe
Principal Investigator:	[name]
Study Duration:	Overall study duration is estimated to enroll for approximately 1 year. Enrollment rate of up to 5 simultaneous patients per site (→ 20 parallel in all 4 sites). Total participation duration: Treatment between 2 days and up to 14 days

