1.1.3. GRV practices

Each site has their own protocol with regard to GRV practice, GRV protocol can vary with regards to the frequency, duration, volume, extraction technique and even what is done with the GRV once extracted.

For example, one site may perform GRV with a 100cc syringe every 4 hours. Promptly returning the suctioned GRV to the patient at the end of the procedure. While another site may connect a bag to the patient's feeding tube and hang it below the height of the patient's bed to slowly empty out the entire content of the patient's stomach over a two hours period, and discard it.

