2.3 Length of stay:
Sample size rationale:

The rationale for sample size calculation is based on a difference in length of stay between the tested group (with smART+ System) and the current standard practice (group B).

Sample size justification:

The comparison between groups in ventilation days is reflected by Effect size.

A sample size of 100 in each group will have 90% power to detect an **effect size of 0.46** using a two group t-test with a 0.05 two-sided significance level. [1, 2]

References:

9.2 Endpoints analysis:
9.2.1 General:

All measured variables and derived parameters will be listed individually and, if appropriate, tabulated by descriptive statistics.

 ART MEDICAL PATIENT SAFETY TECHNOLOGY	Number: CRO-C-2822	Date issued: 01-Mar-2021
	Rev.06	Page 31 of 35

Subject: smART Plus Comparative Study Protocol - Beilinson

For categorical variables summary tables will be provided giving sample size, absolute and relative frequency and 95% CI (Confidence Interval) for proportions by study arm.

For continuous variables summary tables will be provided giving sample size, arithmetic mean, standard deviation, coefficient of variation (CV%), median, minimum and maximum and 95% CI (Confidence Interval) for means of variables by study arm.

All tests will be two-tailed, and a p value of 5% or less will be considered statistically significant.

The data will be analyzed using the SAS® version 9.4 (SAS Institute, Cary North Carolina).

9.2.2 Primary endpoint:

The two-sample T-test or Non-parametric Wilcoxon-Mann-Whitney Rank sum test for independent samples (as is appropriate) will be applied for testing the statistical significance of the difference in feeding efficiency between the study groups.

9.2.3 Secondary endpoints:

- The two-sample T-test or Non-parametric Wilcoxon-Mann-Whitney Rank sum test for independent samples (as is appropriate) will be applied for testing the statistical significance of the difference in number of ventilation days (Evaluated by the number of hours of etCO2 from the hospital electronic records) between the study groups.

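### Randomisation is stratified by APACHE and meant to balance on site, but the planned tests adjust for neither; if those factors predict outcome, the tests are conservative and forgo some power.

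*Combined protocol and SAP*

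**What the plan says.** Section 5.1 sets out the allocation: "Study participants will be randomly assigned to open-label study groups, in randomization ratio of 1:1". It adds two balancing requirements: "the study randomization shall be stratified according to APACHE score measured at baseline", and "The ratio between treated and control groups should be balanced on each site". It gives no APACHE cut-points, number of strata, block size or method for achieving site balance. The synopsis (Study Duration) implies four sites: "20 parallel in all 4 sites".

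For the primary endpoint, section 9.2.2 says: "The two-sample T-test or Non-parametric Wilcoxon-Mann-Whitney Rank sum test for independent samples (as is appropriate) will be applied", the purpose being "testing the statistical significance of the difference in feeding efficiency between the study groups". Section 9.2.3 uses the same pair of tests for ventilation days, nursing time and volumes for gastric residuals (GRV), the urine-monitoring assessment and ICU length of stay. It uses chi-square or Fisher's exact test for ventilator-associated events (VAE). No APACHE, stratum or site term appears anywhere in section 9.

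Section 9.1 powers the primary comparison with the same unadjusted t-test: 50 per group, effect size 0.70, two-sided 0.025, 90% power.

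On whether site could matter, section 1.1.3 notes: "Each site has their own protocol with regard to GRV practice". Section 2.1 counts feed discarded with the GRV in assessing intake, and makes net nutrition delivered the numerator of feeding efficiency.

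**The concern.** Balancing the arms on a prognostic factor removes that factor's contribution to the chance difference between arms. A two-sample test does not know this. Its standard error still contains the between-stratum variance, so it overstates the uncertainty of the treatment contrast. The true type I error then sits below nominal, and power sits below that of an analysis containing the same factors.

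The documents give some reason to expect site to matter. GRV handling differs between sites and feeds into the primary variable, and section 5.3 leaves control care to local practice. By stratifying on APACHE, the plan already treats severity as worth controlling.

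What is at stake is efficiency, together with a clear main analysis. In an open-label trial with an interim look, leaving adjustment unspecified also leaves room for a later choice between adjusted and unadjusted results.

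**Working it through.** **Inputs from the documents.** 50 per group, effect size d = 0.70, two-sided 0.025 and 90% power (9.1); 1:1 allocation, stratified by APACHE, with site balance (5.1); four sites (synopsis).

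**Assumptions not in the documents.** R², the share of outcome variance explained by the APACHE and site strata, is taken as 0%, 10%, 20% and 30%. Two APACHE strata and permuted blocks of 4 are assumed for the simulation.

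**Step 1: the plan's own figure.** With z = 2.241 for two-sided 0.025, d√(n/2) = 0.70 × √25 = 3.50. Normal-approximation power is Φ(3.50 − 2.241) = 89.6%, and the exact noncentral t gives 88.8%. The stated 90% reproduces for the unadjusted test.

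**Step 2: effect of balance.** With exact balance within strata, the variance of the difference in means is 2(1 − R²)σ²/n, while the two-sample test estimates 2σ²/n. Hence:
- unadjusted true alpha = 2[1 − Φ(z/√(1 − R²))]
- unadjusted power = Φ((d√(n/2) − z)/√(1 − R²))
- adjusted power = Φ(d√(n/2)/√(1 − R²) − z)

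For R² = 20%, √0.8 = 0.894. True alpha is 2[1 − Φ(2.506)] = 1.2%. Unadjusted power is Φ(1.407) = 92.0%, and adjusted power is Φ(3.913 − 2.241) = 95.3%.

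| R² | True alpha, unadjusted: formula / simulated | Power at 0.70, unadjusted: formula / simulated | Power at 0.70, adjusted: formula / simulated |
|---|---|---|---|
| 0% | 2.5% / 2.5% | 89.6% / 89% | 89.6% / 89% |
| 10% | 1.8% / 1.9% | 90.8% / 90% | 92.6% / 92% |
| 20% | 1.2% / 1.2% | 92.0% / 91% | 95.3% / 95% |
| 30% | 0.7% / 0.8% | 93.4% / 92% | 97.4% / 97% |

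The simulation compares the t-test with a stratum-adjusted linear model. Repeat runs differ by up to 0.2 points on type I error and about one point on power. The adjusted model's type I error stayed between 2.3% and 2.8%.

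**Step 3: smaller effects.** At d = 0.50 (illustrative; not a planning value), simulated power for R² of 10%, 20% and 30% is 59%, 59% and 61% unadjusted against 63%, 69% and 76% adjusted.

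**Step 4: ventilation days and length of stay.** With 100 per group, d = 0.46 and two-sided 0.05, the stated 90% also reproduces (90.2% normal, 89.9% exact t). By the same formulas, true alpha for R² of 10%, 20% and 30% is 3.9%, 2.8% and 1.9%. Power is 91.4%, 92.6% and 93.9% unadjusted against 92.9%, 95.3% and 97.3% adjusted.

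**Step 5: site variation in controls only.** In the extreme case where site explains 10%, 20% or 30% of control-arm variance and none in the treated arm, simulated power at 0.70 with 50 per group is 88.1%, 88.2% and 88.6% unadjusted against 88.7%, 89.3% and 90.3% adjusted. Adjusted type I error is then itself a little low, at about 1.9% to 2.1%.

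**The case against.** The strongest reply is that nothing promised is lost. The plan claims 90% power for the unadjusted test at 0.70, and that test essentially delivers it at every R² shown. At full enrolment (100 per group) unadjusted power at 0.70 and two-sided 0.025 is already 99.6%, so adjustment has almost nothing to add there. This stands. The gain is relative to an adjusted analysis, and it matters mainly at the 50-per-group look or if the true effect is below 0.70.

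Second, the consequence is conditional. No passage gives an R² or links APACHE to feeding efficiency, and section 2.1 drops days when feeding was stopped by medical order, which may remove some severity-related variation. This stands too: at R² = 0 the two analyses perform alike.

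Third, the GRV argument may apply mostly to controls, because the system has its own GRV set (1.3) and compensates for discarded feed (1.7). The gain from an additive model then shrinks to about 1 to 2 points. That tempers the size but gives no reason to leave the factors out.

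Fourth, section 5.1 gives a site-balance aim without a mechanism. The strata and blocks used above are therefore assumptions, and looser balance would weaken the conservatism.

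A reader might also infer that the mismatch makes the test invalid or produces false positives. The direction is the opposite: a significant unadjusted result would stand. Nor can one say that the reported interval for the treatment effect is too wide. Section 9.2.1 plans intervals by study arm and none for the difference.

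**Conclusion.** The mismatch between allocation and analysis is plain in the text. Its consequence depends on APACHE or site being prognostic, which is plausible for site but not quantified. If the factors explain 10% to 30% of the variance, the primary test at 50 per group runs at about 1.9% to 0.8% instead of 2.5%, and gives up roughly 2 to 5 points of power at 0.70, with more at smaller effects. If they explain nothing, nothing is lost. If site variation sits mainly in controls, the gain is about 1 to 2 points.

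Two stronger readings are not supported: that the trial falls short of its planned power, and that the stated alpha is unconditionally not the one used. Section 9.1 works at 0.025 while section 9.2.1 sets 5% for all tests. That inconsistency is separate and is not caused by stratification; the conservatism described here arises at either level. The point is a low-cost improvement and does not undermine the design.

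**What to change.** - In 9.2.2, and for the continuous between-group comparisons in 9.2.3, make the main analysis a linear model with treatment, baseline APACHE and site. State whether APACHE enters as the score or as the randomisation stratum. If ranks are used, specify a van Elteren test stratified by the randomisation factors.
- For VAE, use a Cochran-Mantel-Haenszel test or a logistic model with the same factors.
- Prespecify a rule for pooling small sites or strata. Under the assumed eight strata, 100 patients average 100/8 = 12.5 per stratum. Site sizes will also be uneven, since the synopsis assigns 100 of about 200 patients to one site.
- In 5.1, state the APACHE cut-points and how site balance is achieved, so that the model matches the allocation.
- Keep the unadjusted tests as sensitivity analyses.

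The cost is wording only. APACHE and site must already be recorded to randomise, and no extra patients are needed. If the factors turn out not to be prognostic, the price is negligible: at R² = 0 and effect size 0.60, simulated power with 50 per group is 77.2% either way.

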5.2. Group A- Interventional Device ("Treated")

Following the screening procedure, staff will utilize the smART+ System to provide feeding optimization to the patient. Feeding tube insertion and commencement of feeding should be done per patients' need and per local hospital procedures.

5.2.1. Videotaping of subject- group A

Following the completion of the informed consent procedure and prior to feeding tube placement, a video recording of the patient will commence. The camera will be placed behind/near the patient head, allowing recording of movements of the feeding tube and medical procedures for later comparison with the data logs recorded by the smART+ console. All recorded data must be attached to the patient files and serves as an integral part of the analyzable data for the study. The video recording is not binding and the PI or the sponsor may choose not to video a specific patient at certain times or at all.

5.2.2. Connecting the patient to the smART+ System

The patient should be connected up to all applicable modules of the smART+ as soon as possible after being enrolled in the study. Connection and use of the smART+ UrineFlow system will be as needed according to PI decision.

Detailed instructions of how to connect a patient to the system can be found in the smART+ User Manual and the accompanying Quick Guides.

5.2.3. Feeding insertion- group A

Study staff should follow the device instructions for use and specific instructions provided by the console during initial tube placement. Time of tube placement is recorded by the console. Once initial placement is confirmed by the system, verification of correct placement should

 ART MEDICAL PATIENT SAFETY TECHNOLOGY	Number: CRO-C-2822	Date issued: 01-Mar-2021
	Rev.06	Page 19 of 35

Subject: smART Plus Comparative Study Protocol - Beilinson

be performed according to hospital procedures (such as abdominal /chest X-ray /other gold standard).

5.2.4.Vital signs- group A

Vital signs (e.g., temperature, pulse, respirations, blood pressure) should be noted within 10 minutes of feeding tube insertion.

5.2.5.REE measurement- group A

Once the patient has recovered from the process of inserting the feeding tube, a baseline REE measurement should be taken using the smART+ flow sensor and CO₂ sensor.

5.2.6.Feeding program- group A

Once the REE measurement is accomplished, personnel authorized by the hospital should program a suitable feeding program using the smART+ Console and in accordance with hospital procedure.

5.2.7.Ongoing use- group A

If system alerts of tube displacement during ongoing use, the need for tube reinsertion/repositioning should be evaluated and performed as needed.

If system alerts an increase in REE, the message should be evaluated by personnel authorized by the hospital, who should decide if to change the patient's feeding program.

5.2.8.Data recording- group A

The following information will be acquired from the patient's medical chart (recorded in the hospital sources) into the eCRF, for each patient

- Initial screening: as detailed in the study eCRF
- Feeding information: Food types, amounts, rate, water delivery, parenteral nutrition, TPN, other nutritional data
- Gastric residual volume: discard gastric residuals amount, GRV procedure times.
- Medications provided: as detailed in the study eCRF.
- Lab results: patient lab results, as detailed in the study eCRF, and obtained 24 hours prior the feeding tube insertion and during the study, should be recorded in the eCRF.
- Imaging: (X-ray, CT, and alike) performed during the study should be obtained and attached to the eCRF.
- Urine: amounts, rates, times, warnings
- ICU submission and discharge ordering times
- Breathing data reports starting from the ICU admission (FiO₂, PEEP)
- Demographics

The following information will be recorded by the smART+ console (or accompanying recording equipment) and extracted directly by the sponsor:

 ART MEDICAL PATIENT SAFETY TECHNOLOGY	Number: CRO-C-2822	Date issued: 01-Mar-2021
	Rev.06	Page 20 of 35

Subject: smART Plus Comparative Study Protocol - Beilinson

- Urine monitoring: amounts, rates, times, warnings, trends (and all other data collected by the smART+ System).
- Feeding information: Food types, amounts, rate, fluids delivery (and all other data collected by the smART+ System).
- Gastric residual volume: GRV amounts and times
- Reflux and position data
- REE data
- Breathing data (collected by the smART+ System)
- All other data collected by the smART+ System.

